### 9.3. Data sources

### 9.3.1. Optum Research Database (ORD)

### **Commercial Claims Data**

Optum has access to a proprietary research database containing medical and pharmacy claims with linked enrollment information with data covering the period from 1993 to current. For 2011, data relating to approximately 12.8 million (actual=12,818,738) individuals with both medical and pharmacy benefit coverage are available. An additional 10.4 million (actual=10,424,191) enrollees with medical benefits only are available. Underlying information is geographically diverse across the United States and fairly representative of the U.S. population. Of the 12.8 million individuals, race/ethnicity and financial resource information was available for approximately 75-85 percent of the individuals.

Claims for pharmacy services are typically submitted electronically by the pharmacy at the time prescriptions are filled. The claims history is a profile of all outpatient prescription pharmacy services provided and covered by the health plan. Pharmacy claims data include drug name, dosage form, drug strength, fill date, days of supply, financial information, and de-identified patient and prescriber codes, allowing for longitudinal tracking of medication refill patterns and changes in medications.

Medical claims or encounter data are collected from all available health care sites (inpatient hospital, outpatient hospital, ER, physician's office, surgery center, etc.) for virtually all types of provided services, including specialty, preventive and office-based treatments. Medical claims and coding conform to insurance industry standards. Claims for ambulatory services submitted by individual providers, e.g., physicians, use the Health Care Financing Administration (HCFA)-1500 or Centers for Medicare and Medicaid Services (CMS)-1500 formats. Claims for facility services submitted by institutions, e.g., hospitals, use the Uniform Billing (UB)-82, UB-92, UB-04, or CMS-1450 formats. Medical claims include: multiple diagnosis codes recorded with the ICD-9-CM diagnosis codes; procedures recorded with ICD-9-CM procedure codes, Current Procedural Terminology (CPT), or Healthcare Common Procedure Coding System (HCPCS) codes; site of service codes; provider specialty codes; revenue codes (for facilities); paid amounts; and other information. Typically, facility claims do not include medications dispensed in hospital. Approximately six months following the delivery of services is required for complete medical data.

Pharmacy claims are typically added to the research database within six weeks of dispensing. Approximately six months following the delivery of services are required for complete medical data.

### Medicare Advantage and Part D Data

Medical and pharmacy claims data are available for approximately 3.6 million enrollees since 2006 that are enrolled in Medicare Part C (commonly referred to as the Medicare Advantage program) through an offering associated with Optum. Prior to 2006, data were available for approximately 500,000 of these enrollees. In addition, approximately five million enrollees in a Medicare Part D benefit have pharmacy claims data available for each year since the start of the program in 2006. Medicare Advantage enrollees choose to receive all of their health care services through a provider organization in lieu of Medicare Part A/B coverage (commonly referred to as Medicare Fee for Service).

There are certain limitations related to pharmacy claims for the Medicare Advantage population prior to 2006. Prior to 2006, managed Medicare enrollees in the plans affiliated with Optum had pharmacy coverage through their health plan—one of the benefits of enrollment in a managed Medicare plan. For approximately 25 percent of these enrollees, these pharmacy benefits had caps on expenditures. Enrollees with substantial pharmacy expenditures may have exceeded their cap in certain years. For these members, in most cases, it is expected that additional filled prescriptions will not be observed in the claims data.

Beginning in 2006, complete medical and pharmacy information is available for Medicare enrollees with medical and Part D coverage (MAPD). Pharmacy claims contain sufficient information to trace patients' pharmacy expenditures through the multiple phases of the Part D plans.

### 9.3.2. Mortality Data

By linking external mortality data to ORD, it is possible to determine the timing of deaths that are not otherwise captured in the claims. After subjects are linked, these data can be used to inform sample selection. That is, subjects that might otherwise be removed from the study due to insufficient continuous enrollment may be included if they were observed to have disenrolled because of death. Mortality data can also be used to modify outcomes and other study endpoints.

Mortality information is sourced from the SSA death files. The SSA files, with a proper linkage, allow establishment of the date of death. They do not, however, include information on cause of death. Month and year of death are available for individuals 18 years of age and older only. Approval through the Optum data disclosure analysis process is required for the use of the exact date of death (month, day, and year) and requires an additional processing fee.

### 9.3.3. Socioeconomic Status Data

In addition, to allow for more powerful insight into prevalence and burden of illness, Optum has a unique source of individual-level data which can be linked to ORD that allows for analysis of socioeconomic characteristics. Specifically, these data elements include race/ethnicity, language preference, occupation, household income category, and household

net worth category. The data populating these socioeconomic elements are generated by a combination of self-report, modeling, census data, and a variety of other individual-level and population-level data sources. Certain data elements may be missing for some individuals in the claims database. The most complete variables such as race/ethnicity and income category are populated for approximately 75-80 percent of patients. These data have been used extensively in market analyses and population segmentation analyses. While these data have application to health economics and outcomes research, certain limitations are associated with these data, including inaccuracy in assignment of socioeconomic status, missing data, and predefined categorizations (e.g., income level).

### 9.3.4. Medical Chart Data

The claims database analysis will be supplemented with abstracted medical chart data for a subset of study subjects. The medical chart data will come from a medical chart review of patients identified explicitly for this study from the administrative claims research database, following receipt of the appropriate approvals. The hospital or medical facility where each index ACS-PCI hospitalization took place will be identified using the administrative claims data. The facility most relevant for the study will be identified for each patient. Facilities will be invited to participate in the study and contacted to make arrangements for the medical chart review.

Because study subjects will be selected from ORD, the study concept and any communication with health care providers must be approved by the large U.S. health plan affiliated with Optum. Optum will submit a study synopsis and network physician study-related communication materials to the health plan for review. Following health plan approval, the study will be submitted for institutional review board (IRB) and privacy board review. Optum will communicate directly with the IRB and privacy board to address any questions and/or provide any additional information in connection with the reviews. Lilly shall provide any necessary assistance or documents required for the submission to the IRB and privacy board. Approval from an IRB or privacy board for this study is not guaranteed. Optum will initiate medical chart abstraction activities only after the study protocol and study documents have been approved and Optum is granted a Waiver of Authorization by the privacy board and a waiver of the informed consent requirement by the IRB. Upon receipt of the Waiver of Authorization from privacy board, Optum will provide a copy of the waiver document and general study information to the relevant data sources for approval to utilize such data source's data in the study, which is not guaranteed.

Following health plan, IRB, and privacy board approvals, Optum will send a research study notification letter to the health plan market medical directors (MMDs) to alert them of a medical chart review study being conducted in the field. The MMDs will each receive an email containing a study synopsis, a copy of the network physician abstraction request letter, and a list of providers/medical facilities that will be contacted for participation in their market. Upon completion of the study, Optum will share published study results with the MMDs.

### 9.4. Study size

The following sample size and power calculations are for the claims database analysis, the primary data source for this study. The subset of patients selected for chart abstraction (medical chart review) will not provide adequate statistical power for outcomes comparisons.

Table 2 provides preliminary sample sizes available in the Optum Research Database for commercial and Medicare Advantage health plan enrollees between July 1, 2009 and June 30, 2013 with the following study criteria: 1) at least one ACS hospitalization, 2) at least one ACS hospitalization with PCI procedure codes during the same hospitalization, 3) at least one ACS-PCI hospitalization with a fill for prasugrel or clopidogrel within 30 days post-discharge, 4) continuously enrolled for 12 months before the admission date and six month after discharge from the ACS-PCI-ADP hospitalization, and 5) with no baseline TIA or stroke were identified (n=27,284). Among these, 5,101 (19%) had at least one fill for prasugrel, 21,548 (79%) had at least one fill for prasugrel and clopidogrel within 30 days post-discharge the ACS-PCI hospitalization.

Steps	Subset of Step	Criteria	Count
		At least one inpatient hospitalization with ACS diagnosis codes	
		in the primary or secondary position	
		plus	
		PCI procedures codes	
		plus	
		At least one fill for prasugrel or clopidogrel within 30 days	
		post-discharge from the ACS-PCI hospitalization	
		plus	
		Continuously enrolled at least 365 days before the admission	
		and 180 days after discharge from the	
		ACS-PCI-ADP hospitalization	
	ACS + PCI + ADP-ri	plus	
1	+ CE + no TIA/stroke	No baseline TIA/stroke	27,284
		- Prasugrel	5,101
		- Clopidogrel	21,548
		- Prasugrel and clopidogrel	635

 Table 2. Number of Patients Available for Analysis (July 1, 2009 – June 30, 2013)

These counts are for informational purposes only and may not represent the actual number of enrollees available for analysis. Application of other selection criteria required for this study or other factors may further reduce the available sample size. However, for the primary population, ACS-PCI patients with no history of TIA or stroke, treated with prasugrel or clopidogrel post-discharge from the index hospitalization (Table 2), the above sample sizes will provide 92% power at a 0.05 two-sided significance level to detect a 15% reduction in the adjusted hazard ratio (HR=0.85), assuming a clopidogrel base rate of 12% for MACE up to one year after the index hospitalization discharge and a 3:1 clopidogrel to prasugrel ratio. Of note, the study power

will vary as a function of both the clopidogrel event rates (as shown in Figure 2) and the magnitude of the treatment effect.

### Figure 2. Sample Size Calculation for 80% Power

### 9.5. Data management

Datasets and analytic programs will be exclusively maintained, accessed, and analyzed by researchers at Optum. No patient level data will be transferred to the study sponsors. All data will be stored according to Optum's procedures.

### 9.6. Data analysis

### 9.6.1. Missing Data

No imputation of missing data will be conducted for outcome variables. For covariates, missing data may be addressed through methods such as creation of missing data categories (for categorical variables). This will be done to avoid selection bias that can occur by deleting cases with missing variables of interest. Details will be provided in the statistical analysis

plan. Sensitivity analysis may be considered if the amount of missing data is substantial (>20%).

## 9.6.2. Descriptive Analyses

Demographic, clinical, and other baseline variables (including resource use and cost) will be summarized by cohort and for overall group as the counts and percentages for categorical variables and means, median, standard deviation, min, and max for continuous variables. Differences between cohorts will be assessed using Chi-square test for categorical variables and t-test and ANOVA for continuous variables. Exact tests, bootstrapping and/or nonparametric tests will be used as appropriate. All tests will be two-sided.

# 9.6.3. Unadjusted Outcomes Analyses

Unadjusted outcomes and treatment patterns will be compared using the same methods described in the descriptive analyses section above. In addition, Kaplan-Meier curves along with log rank tests will be used to evaluate persistence (time to discontinuation), switching (time to), survival (time to death), and time to first occurrence of a major adverse cardiovascular event.

# 9.6.4. Propensity Score Creation

The propensity score adjustment methodology has been widely used in observational studies for causal inference ever since it was introduced by Rosenbaum and Rubin in 1983. Propensity score matching will be the primary analysis. However, if propensity score matching cannot produce balanced matched cohorts with at least 90% of the prasugrel sample, then propensity score stratification will be considered.

### Propensity score matching

Matching on propensity score can achieve a very high degree of balance between comparison groups and therefore, can mitigate confounding by baseline characteristics that may independently affect outcomes of interest. A propensity score for each subject will be defined as the probability of being in the prasugrel cohort and estimated using logistic regression. Prasugrel and clopidogrel subjects may be matched on their propensity scores using a greedy or optimal method to adjust for potential confounding bias.

The first step in the primary (propensity adjusted) analysis will be to estimate propensity scores for each patient using a forward step-wise logistic regression model with prasugrel cohort membership as the binary outcome measure and baseline demographic and clinical characteristics and baseline treatment utilization measures as the independent variables in the

<sup>15 Rosenbaum PR and Rubin DB. The central role of the propensity score in observational studies for causal effects. Biometrika. 70(1):41–55, 1983.

<sup>16 Rosenbaum PR, Rubin DB. Reducing bias in observational studies using subclassification on the propensity score. J Am Stat Assoc 1984; 79:516-24.

<sup>17 Rubin DB. The design versus the analysis of observational studies for causal effects: parallels with the design of randomized trials. Stat Med 2007; 26:20-36.

model. These independent variables will be selected *a priori* based on literature and expert opinion as potential confounds (i.e., factors related to both cohort and outcome). The final list of independent variables to be included in the propensity score model will be determined following review of the baseline descriptive statistics. A 0.10 significance level will be used for independent variables entering and remaining in the model.

The step-wise regression model building process will begin by evaluating each of the candidate independent variables and selecting the variable with the largest score chi-square statistic. If the p-value for this variable is less than the pre-specified model building significance level (0.10), then this variable will be entered into the propensity model (logistic regression model) as the 1st independent variable. At step 2, the score chi-square statistic for each remaining candidate variable will be evaluated and the variable with the largest test statistic will then also added to the propensity model as long as its p-value is less than 0.10. Before moving to step 3, the chi-square p-value for each variable in the propensity model will be re-examined (because values from existing variables in the model may change once the new variable is introduced) and the variable will be removed from the model if the p-value was no longer < 0.10. This process will be continued until all candidate independent variables are entered in the model or until none of the remaining candidate independent variables met the 0.10 significance level requirement for entering the model.

If using greedy or optimal matching, prasugrel and clopidogrel subjects will be matched 1:1-1:3. Subjects not matched may be excluded from analysis. The success of the matching procedure will be evaluated by comparing the post-matched characteristics included in the propensity score model. Model modifications may be needed to increase sample size or

<sup>18 Bae JP, Ernst FR, Lipkin C, et al. Hospitalization Costs of Acute Coronary Syndrome Patients Undergoing Percutaneous Coronary Intervention: A Comparison Between Clopidogrel and Prasugrel Patients in a US Hospital Database. Abstract 730. 2012 Transcatheter Cardiovascular Therapeutics Annual Meeting, Miami, FL.

<sup>19 Bae JP, Faries DE, Ernest FR et al. Assessment of 30-Day Rehospitalization for Acute Myocardial Infarction in Patients with Acute Coronary Syndrome Who Received Percutaneous Coronary Intervention: A Comparative Effectiveness Study of Clopidogrel and Prasugrel. Abstract TCT-53. 2012 Transcatheter Cardiovascular Therapeutics Annual Meeting, Miami, FL.

<sup>20 Cohen, M. Predictors of bleeding risk and long-term mortality in patients with acute coronary syndromes. *CMRO*. 2005;21(3): 439–445.

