### Baseline

12 months before the index hospitalization admission date.

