## 5. Abstract

- Title: One Year Post-discharge Clinical and Economic Outcomes among Patients with ACS Managed with PCI and Treated with Prasugrel vs. Clopidogrel
- Rationale and background: While the results from the TRITON-TIMI 38 established the superior anti-thrombotic efficacy of prasugrel in combination with aspirin over clopidogrel plus aspirin, there is currently insufficient long-term real-world data that directly compares the clinical and economic outcomes of prasugrel and clopidogrel patients. This retrospective claims database analysis supplemented with a medical chart review for a subset of patients will help to fill in this important gap in the literature.
- Research Objectives: The primary study objective is to compare major adverse cardiovascular events (MACE) up to one year of hospital discharge among ACS patients with no history of TIA or stroke, managed with PCI, and treated with prasugrel vs. clopidogrel. Secondary objectives are to compare demographics, baseline clinical characteristics, treatment patterns, and clinical and economic outcomes up to one year of hospital discharge among ACS patients with no history of TIA or stroke, managed with PCI, and treated with prasugrel vs. clopidogrel.
- Study design: Retrospective cohort study
- Population: The primary study population will include ACS patients with no history of TIA or stroke, managed with PCI, and treated with prasugrel vs. clopidogrel. Subgroups with other important characteristics (age, gender, comorbidities of interest) will be defined in the SAP.
- Variables: The primary dependent variable will be major adverse cardiovascular events (MACE) through one year of hospital discharge. Secondary dependent variables will include clinical and economic outcomes, and treatment patterns during index hospitalization and through three months and one year post-discharge from the index hospitalization. Study timeframes will be finalized in the SAP. The primary independent variable will be treatment cohort (prasugrel vs. clopidogrel) and other independent variables (covariates) will include demographics, baseline clinical characteristics, and baseline treatment utilization.
- Data sources: Optum Research Database supplemented with medical chart review for a subset of patients.
- Study size: Refer to section 9.4 for preliminary sample sizes in the Optum Research Database (ORD). Final sample size will be known after applying all selection criteria.

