### 8.2. Secondary Objectives

- 2. To compare demographics and baseline characteristics between patients treated with prasugrel versus clopidogrel before propensity adjustment.
- 3. To compare index therapy treatment patterns with prasugrel versus clopidogrel including adherence, discontinuation, persistence, and switching as listed in Table 1 through 1) three months and 2) one year post-discharge from the index hospitalization.
- 4. To compare NACE and its components with prasugrel versus clopidogrel including bleeding as listed in Table 1 through 1) 30 days, 2) three months, and 3) one year post-discharge from the index hospitalization.
- 5. To compare all-cause health care resource utilization (including length of stay of the index hospitalization and subsequent readmissions) and costs with prasugrel versus clopidogrel through 1) 30 days, 2) three months, and 3) one year post-discharge from the index hospitalization. Resource utilization and costs will be stratified as listed in Table 1.
- 6. To compare disease-related (including MI, revascularization, stroke, unstable and stable angina, congestive heart failure, and bleeding as listed in Table 1) health care resource utilization and costs with prasugrel versus clopidogrel through 1) 30 days, 2) three months, and 3) one year post-discharge from the index hospitalization.
- 7. If differences in treatment patterns (i.e, adherence, persistence, switching, and discontinuation) are found, then assess factors associated with adherence, persistence, switching, and discontinuation of a) prasugrel and b) clopidogrel patients through one year post-discharge from the index hospitalization.
- 8. If differences in treatment patterns are found, then examine associations between treatment patterns (adherence, persistence, switching, and discontinuation) and outcomes (clinical: all-cause mortality, MACE, inpatient readmissions; economic: total costs) for a) prasugrel and b) clopidogrel patient through one year post-discharge from the index hospitalization.

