### 8.3. Exploratory Objectives for Medical Chart Review

- 9. The abstracted medical chart data gathered for a subset of patients in the claims database analysis will be used to:
  - Identify new confounders not available in the claims such vital statistics (e.g., weight, smoking status) and inpatient treatment (e.g., ADP-ri, aspirin dose, CABG, type and number of stents, number of vessels)
  - Confirm the accuracy of the measured confounders in the claims including medical histories (in particular, history of TIA and stroke) and prior procedures
  - Compare the ADP-ri treatment administered during the index hospitalization to the first ADP-ri therapy identified post-discharge in the claims
  - Validate the claims-based major/severe bleeding algorithm
- 10. To compare stent thrombosis-related health care resource utilization through 1) three months and 2) one year post-discharge from the index hospitalization.

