6, 7	Post-discharge resource utilization	PPPM number of all-cause and disease-related health care         utilization during one year post-discharge from the index         hospitalization (n, %, mean, SD, median)         - Inpatient admissions         - Length of stays         - ICU/CCU stays         - Length of ICU/CCU stays         - Outpatient hospital visits         - Physician office visits         - Family/general practice         - Cardiology         - Endocrinology         - Other specialties         - Emergency department visits	Y	Ν
	Post-discharge resource costs	PPPM all-cause and disease-related costs (mean, SD, median)         during one year post-discharge from the index hospitalization:         -       Total (medical + pharmacy costs)         -       Medical costs         -       Inpatient costs         -       Emergency department costs         -       Outpatient hospital costs         -       Physician office visits         -       Family/general practice         -       Cardiology         -       Endocrinology         -       Other specialties         -       Other medical encounters         -       Pharmacy costs	Y	N
10	Index	PCI procedure during the index hospitalization (n, %)	Y	Y
(See Medical Chart Abstraction Form for complete list of	hospitalization revascularization	Stent implantation (n, %) - DES, BMS, unknown, none	Y	Y
		- 1, 2, 3, 4+ Number of vessels (n, %)	Y	Y
index		- 1, 2, 3, 4+		
variables)		CABG during the index hospitalization (n, %)	Y N	Y
		admission (mean, SD, median)	IN	Ŷ
	Index hospitalization	ACS diagnosis during the index hospitalization (n, %) - STEMI, NSTEMI, UA	Y	Y
		Days during index hospitalization (mean, SD; median)	Y	Y
		Days during ICU/CCU index hospitalization (mean, SD; median)	N NI	Y
		and PCI (mean, SD, median) Initial and discharge dose amounts of prasugrel and clopidogrel	N N	Y Y
		% with loading dose Hospital characteristics (n. %, mean, SD, median)	Y	N

OBJECTIVE	VARIABLE	DEFINITION	CLAIMS	CHART
		- urban/rural		
		Medications administered during the index hospitalization (n, %)	N	Y
		
 
ADP-ri, aspirin, glycoprotein IIb/IIIa inhibitors
 
		
		(abciximab, eptifibatide, tirofiban), fibrinolytic therapy,		
		anticoagulant (unfractionated heparin, LMWH		
		(dalteparin, enoxaparin, tinzaparin), fondaparinux), direct		
		thrombin inhibitor (bivalirudin), other anticoagulant or		
		antithrombin (rivaroxaban, dibigatran, apixaban,		
		coumadin)		

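### The stated propensity covariates stop at admission, so adjustment for index ACS type and PCI features is not assured; index length of stay and bleeding are compared by a drug filled afterwards

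*Protocol*

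**What the plan says.** **Covariates.** Section 9.6.4 of the protocol names the propensity inputs as "baseline demographic and clinical characteristics and baseline treatment utilization measures as the independent variables". The abstract gives the same classes: "other independent variables (covariates) will include demographics, baseline clinical characteristics, and baseline treatment utilization". Section 3 defines baseline as "12 months before the index hospitalization admission date", and section 9.1.4 lists the baseline period and the index hospitalization period as two separate observation periods. The list is not closed: "The final list of independent variables to be included in the propensity score model will be determined following review of the baseline descriptive statistics". Matching success is to be "evaluated by comparing the post-matched characteristics included in the propensity score model".

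**Where the index-stay variables sit.** In Table 1 (section 9.2), the row that opens "ACS diagnosis during the index hospitalization (n" (STEMI, NSTEMI, UA) is in the block labelled objective 10, which points to the chart abstraction form. So are stent implantation by type and number of vessels. All three are marked as available in claims. The objective 2 rows, which list the baseline variables, contain none of them. Section 8.3 instead names "CABG, type and number of stents, number of vessels" among confounders that the claims do not hold. Section 9.1.5 makes index diagnosis a subgroup.

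**In-hospital comparisons.** Section 9.1.2.1 defines the cohorts by the first outpatient fill between discharge and 30 days later. Objective 5 in section 8.2 compares utilization by cohort, "including length of stay of the index hospitalization and subsequent readmissions". Table 1 lists index-stay bleeding under objectives 1, 4, 5 and 10.

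**The concern.** The type of ACS and the extent of the PCI are known before the study index date, which is the discharge date. They may affect both the drug chosen and the risk of MACE. Section 8.3 itself calls the stent and vessel variables confounders. Section 7 reports that a similar ACS-PCI cohort showed marked differences between prasugrel and clopidogrel patients, so channelling is a realistic worry. If the text is followed as written, measured confounders of the primary comparison can be left out of the score and out of the check that is meant to reveal imbalance.

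The second issue is time order. Index length of stay and index bleeding are complete before the fill that assigns the cohort. A bleed or a complicated stay may affect which drug is filled. A cohort difference in these variables then cannot be read as an effect of the drug.

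**Working it through.** **1. The plan's own figure.** Section 9.4 states 92% power for HR 0.85 at two-sided 0.05, with a 12% clopidogrel rate and a 3:1 ratio. Take 5,101 prasugrel patients (Table 2) and 3 × 5,101 = 15,303 clopidogrel patients.

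- Prasugrel risk: 1 − (1 − 0.12)^0.85 = 0.103.
- Events: 5,101 × 0.103 + 15,303 × 0.12 ≈ 2,362.
- Schoenfeld: √(2,362 × 0.25 × 0.75) × |ln 0.85| − 1.96 ≈ 3.42 − 1.96 = 1.46, so power is 92.8%.
- Two-proportion formula on the same risks: 91.6%.

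The stated power reproduces. It assumes an unbiased adjusted hazard ratio, which is the issue here.

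**2. The text on covariates, followed through.**

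- The propensity inputs are baseline variables, and baseline ends at admission. ACS type, stents and vessels belong to the index stay.
- The stated balance check covers variables in the model, so an omitted variable escapes it.
- The logistic sensitivity model in section 9.6.6 reuses the variables of the final propensity model, so it inherits any omission.
- The rule-out analysis in section 9.6.6 is aimed at unmeasured confounders. ACS type is measured.
- Section 8.3 sends stents and vessels to the chart review. Section 9.1.6 describes that as a commercial-only convenience sample of 1,200, and section 9.4 says it is not adequately powered for outcome comparisons.

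**3. Possible size, on assumed inputs only.** The protocol gives no split of ACS type or PCI features by cohort. For one omitted binary factor with prevalence p1 (prasugrel) and p0 (clopidogrel) and relative risk RR for MACE, the apparent hazard ratio at a true null is approximately [1 + p1(RR − 1)] / [1 + p0(RR − 1)].

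| p1 vs p0 (assumed) | Standardized difference | RR 0.67 | RR 2.0 |
|---|---|---|---|
| 35% vs 30% | 0.107 | 0.982 | 1.038 |
| 40% vs 30% | 0.211 | 0.963 | 1.077 |
| 45% vs 25% | 0.429 | 0.928 | 1.160 |

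For example, the last cell is (1 + 0.45) / (1 + 0.25) = 1.160. Multiplied by a true 0.85, the first row gives 0.83 to 0.88 and the last row 0.79 to 0.99. All three imbalances exceed the 0.10 flag in section 9.6.4. The formula gives no credit for matched variables that are correlated with the omitted one, so it tends to overstate the bias where such correlation exists.

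**4. Time order.** The sequence is admission, PCI, any in-hospital bleed, discharge, then a fill on days 0 to 30. Exposure comes last. Section 9.8 bridges this by assuming that the first fill is the drug started in hospital, to be checked in the chart subset. Section 9.6.6 says that the validity of in-hospital outcomes will be reconsidered if switching is high. Agreement between inpatient and outpatient drug would show little switching. It would not show that events of the stay had no part in the choice of drug.

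**The case against.** The strongest reply is that the list is open. Section 9.6.4 selects candidates from literature and expert opinion, defers the final list, and allows model modifications to improve balance. The Cox model in section 9.6.5.2 is multivariate with unnamed covariates, and an exact list commonly belongs in the SAP. Table 1 also uses baseline loosely: its objective 2 rows include index year and age at the study index date. ACS type is a planned subgroup.

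This defeats one reading that a reader might infer, namely that the protocol limits the score to pre-admission variables and leaves ACS type, stents and vessels unadjusted. The document does not say so. What stands is narrower. The deferral works within the classes that the protocol names, and a subgroup analysis does not adjust the overall estimate. The SAP may well include these variables, but the protocol text points away from them.

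On stents, Table 1 is damaged in the copy reviewed. The number-of-stents label is lost, so its claims flag cannot be relied on. The flags for stent implantation and number of vessels are legible, and the conflict with section 8.3 stands for those.

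On the in-hospital comparisons, the protocol discloses its assumption and a check. A reader might infer that cause and effect are shown to be reversed; the documents support only that they may be. Under the section 9.8 assumption, index bleeding and length of stay could be consequences of treatment, which is a sound reason not to force them into the main score.

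**Conclusion.** The point holds in a limited form. As written, the protocol does not provide for adjustment of the overall MACE estimate for index ACS type or PCI characteristics. It marks ACS type, stent implantation and number of vessels as available in claims, and it contradicts itself on stents and vessels. It also compares index length of stay and index bleeding by an exposure defined after they occurred, and the stated assumption and chart check do not resolve that.

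The size of the bias cannot be derived from the documents. On the assumed inputs above it runs from negligible (0.98 to 1.04 at a true null) to large against the 0.85 target (0.93 to 1.16), in either direction. The large values need a wide imbalance and a strong risk factor together, with no help from correlated covariates. The documents therefore do not support a claim that the primary result will be biased by any particular amount. The stated 92% power is not in error. This should be corrected before the propensity model is finalised.

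**What to change.** 1. Extend the covariate window for the propensity model from the 12 months before admission through the index admission and PCI.
2. Include index ACS type (STEMI, NSTEMI, UA) and the claims-available PCI variables (stent implantation and type, number of vessels). Check balance on them whether or not the stepwise rule retains them.
3. Reconcile section 8.3 with Table 1 on which stent and vessel variables the claims hold.
4. Report index length of stay and index-stay bleeding by cohort as description only, and remove them from the treatment-effect comparisons under objective 5 and in Table 1.
5. Adjust for index bleeding and length of stay only in a sensitivity analysis, because they may be post-treatment if the drug was started in hospital.

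Exact matching on ACS type is an option but is not needed to resolve the point.

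The cost is protocol and SAP wording, with no new data. There may be slightly fewer matches, and two in-hospital comparisons become descriptive. At the 90% retention floor in section 9.6.4 (0.90 × 5,101 ≈ 4,591 prasugrel patients, with 3 × 4,591 = 13,773 clopidogrel patients), power under the plan's assumptions would still be about 90% by Schoenfeld and 88.6% by two proportions.
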